4. STUDY DESIGN AND RATIONALE

4.1. Description of Study Design

This is an open-label, single-arm, 3-visit, dispensing clinical trial. Approximately 155 subjects (93 myopes and 62 hyperopes) will be enrolled into the study with the aim of completing approximately 140 subjects (84 myopes and 56 hyperopes).

The study begins with an initial visit, Visit 1 (Day 0), then if a subject is found to meet all eligibility criteria, they will be fit with the study lens in both eyes. Otherwise, the subject will be deemed ineligible and classified as a screen failure and exited from the study.

If a subject is dispensed lenses at the initial visit, then two additional visits will be conducted. Visit 2 will be conducted 7 ± 1 days after Visit 1, where subjects will undergo lens optimization, if needed. Subjects will be dispensed the optimized pair for 7 ± 1 days and return for Visit 3. Study endpoints will be measured, and the subject will be exited from the study.

Subjects will be instructed to wear lenses for a minimum of 6 hours a day, every day between visits. Lost or damaged lenses may be replaced when necessary. Unscheduled visits may be conducted, if necessary.

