14.2. Sample Size Justification

The total sample size of 140 subjects who complete the study (Visit 3) was calculated to provide adequate power in detecting statistical superiority of the Test lens relative to prespecified thresholds for binocular distance, intermediate and near logMAR VA, CLUE vision Scores, Absolute toric rotation, rotational stability, rate of unacceptable lens fitting and rate of grade 3 or higher SLFs. All co-primary effectiveness and safety hypotheses are required to achieve statistical significance for the study objective to be satisfied, therefore no adjustment for multiple primary hypotheses is necessary. Each co-primary hypothesis will be tested using a 1-sided Type I error rate of 0.025.

Thresholds for hypotheses associated with CLUE vision, comfort and, handling scores are from a meta-analysis of 14 JJVCI clinical trials of toric and multifocal toric contact lenses used by habitual contact lens wearers aged 40 to 70 years¹². In this analysis, baseline CLUE scores (for subjects' habitual contact lenses) from 14 clinical studies were analyzed to establish thresholds reflecting the "real-world" performance of contact lenses wearers in this population

JJVC CONFIDENTIAL

with respect to CLUE vision, comfort, and handling scores. Thresholds for all other endpoints were based on clinically relevant margins.

Additionally, this study was also powered to test superiority for secondary endpoints with respect to CLUE vision, comfort and, handling scores and lens fit success using a 1-sided Type I error rate of 0.025. Secondary endpoints will be tested using a fixed sequence approach. Further details on the preservation of the study overall Type I error rate are in Section 14.4.

The sample size of 140 to complete yields at least 81% overall power to detect statistical superiority for all co-primary endpoints. This sample size provides a statistical power of at least 99% for each co-primary and secondary endpoint. To account for subject drop-out approximately 155 subjects will be enrolled to ensure at least 140 subjects complete the study.

Endpoint Domain	Endpoint	Statistical Test Type (Statistically Significantly)	Sample Size	Power (%)
Primary Efficacy	Distance (4m) Binocular Visual Acuity (logMAR)	Superiority: mean VA< 0.00	9	99.1
	Intermediate (64cm) Binocular Visual Acuity (logMAR)	Superiority: mean VA< 0.17	6	99.5
	Near (40cm) Binocular Visual Acuity (logMAR)	Superiority: mean VA< 0.17	29	99.1

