ruore /.	instorical	Data	υ,	Lindpoint

SD: Standard Deviation

*Summaries for primary efficacy and secondary endpoints were provided for the per-protocol population at the 1-week follow-up evaluation.

**Summaries for the primary safety endpoints were provided for the safety population; all available data was included

Co-Primary Efficacy Endpoint Sample Size Calculations:

Distance, Intermediate and, Near logMAR Visual Acuity

Sample size calculations for distance, intermediate and near visual acuity were carried out separately using one-sided, one-sample mean t-test, with a one-sided Type I error rate of 0.025 for each hypothesis using the *One-Sample T-Tests for Superiority by a Margin* procedure in Power Analysis & Sample Size (PASS2021) software Version 21.0.6 (NCSS LLC, Kaysville UT)¹³. To preserve the overall study power, each endpoint was powered to approximately 99%. The assumptions for averages and standard deviations were made based on historical values from previous studies (Table 7).

CLUE Vision Scores (Hyperopes and Myopes)

Sample size calculations for CLUE Vision scores were carried out separately for each sphere stratum (hyperopes and Myopes) using one-sided, one-sample mean t-test, with a one-sided Type I error rate of 0.025 for each hypothesis using the *One-Sample T-Tests for Superiority by a Margin* procedure in Power Analysis & Sample Size (PASS2021) software Version 21.0.6 (NCSS LLC, Kaysville UT)¹³. To preserve the overall study power, each endpoint was powered to approximately 99%. The assumptions for averages and standard deviations were made based on historical values from previous studies (Table 7).

Toric Rotation and Lens Stability

The reference rate for absolute toric lens rotation $\leq 10^{\circ}$ was based on the historical results of 90.2%. The reference rate for lens stability $\leq 5^{\circ}$ was based on the worst-case scenario of 99%, given the historical results show 100%. Toric lens orientation and rotational stability, respectively, are defined as a binary response:

Toric Lens Orientation : Y
=
$$\begin{cases} 1 & \text{if a subject eye has absolute toric lens rotation} \leq 10^{\circ}, \\ 0 & \text{Otherwise} \end{cases}$$

Rotational stability: $Z = \begin{cases} 1 & \text{if a subject eye has lens stability with blinks } \leq 5^\circ, \\ 0 & \text{Otherwise} \end{cases}$

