Grade 3 or Higher SLFs related to study lens wear was converted to a binary response as Y=1, if a subject eye has a clinically significant SLF, and Y=0 otherwise, for analysis purposes. Historical data show *none or an extremely low rate* (<1%) for clinically significant SLFs (Grade 3 or higher) for the test lens. Assuming a correlation of 0.70 between left and right eyes, a total of 5000 replicating trials were simulated with a reference rate of 1% (worse-case scenario). Given the rare event binary outcome of slit lamp findings, each replicated sample was analyzed using a Bayesian beta-binomial model with correlated binary data (Diniz et al; 2010)¹⁴. A non-informative prior distribution, beta (0.5, 0.5) was used to model P_T (proportion of eyes with Grade 3 or higher SLF for the Test lens). For each simulated trial, the 95% central posterior credible interval constructed for the percentage of eyes with grade 3 or higher SLFs for the Test lens was calculated. The null and alternative hypothesis for statistical significance

were $P_T \ge 5\%$ and $P_T < 5\%$, respectively. With the proposed sample size, at least 99% of the estimated 95% credible intervals had the upper bound below 5%.

As indicated in Table 6, co-primary safety endpoints were powered to at least $\sim 89\%$ individually, yielding a combined power of $\sim 88\%$. With respect to co-primary efficacy, each hypothesis, was powered to $\sim 99\%$, which provided a combined power of $\sim 92\%$. Therefore, the overall combined study power for co-primary safety and co-primary efficacy hypotheses is $\sim 81\%$.

Secondary Efficacy Endpoint Sample Size Calculations:

CLUE Vision, Comfort and, Handling (Hyperopes and Myopes)

Sample size calculations for the secondary endpoints of CLUE vision, comfort, and handling scores were carried out separately for each sphere stratum (hyperopes and Myopes) for all three CLUE domains using one-sided, one-sample mean t-test, with a one-sided Type I error rate of 0.025 for each hypothesis using the *One-Sample T-Tests for Superiority by a Margin* procedure in Power Analysis & Sample Size (PASS2021) software Version 21.0.6 (NCSS LLC, Kaysville UT)¹³. The assumptions for averages and standard deviations were made based on historical values from previous studies (Table 7).

Lens Fit Success

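### The combined co-primary powers (about 92% efficacy, about 81% overall) mix powers at n=6 to 29 with powers at n=140, so they understate the planned design: about 96-97% and 85-86%.

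*Combined protocol and SAP*

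**What the plan says.** Section 4.1 sets the target as the "aim of completing approximately 140 subjects (84 myopes and 56 hyperopes"). Section 14.2 states: "Each co-primary hypothesis will be tested using a 1-sided Type I error rate of 0.025". All nine co-primary tests must succeed.

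For acuity and CLUE vision, 14.2 says: "To preserve the overall study power, each endpoint was powered to approximately 99" per cent. Table 6 gives the sample size at which each of these endpoints reaches that power. The distance acuity row reads "Superiority: mean VA< 0.00 9 99.1" (n, then power in per cent) and the intermediate row "Superiority: mean VA< 0.17 6 99.5". Near acuity is at n=29, CLUE vision in myopes at n=29 and CLUE vision in hyperopes at n=23. The remaining co-primary rows are all at n=140: absolute rotation >99%, stability with blinks 96.8%, Grade 3 or higher slit-lamp findings 89.3%, unacceptable fit >99%.

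The combined figure appears twice in 14.2. Before Table 6: "The sample size of 140 to complete yields at least 81% overall power to detect statistical superiority for all co-primary endpoints". After the safety calculations, about 88% for safety and about 92% for efficacy lead to: "Therefore, the overall combined study power for co-primary safety and co-primary efficacy hypotheses is" about 81%.

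**The concern.** Success is defined as winning all nine tests, so joint power is the main justification for the sample size. The closing statement gives about 92% and about 81% as the power of the study, but five of the nine factors belong to trials of 6 to 29 subjects. A joint power should take every factor at the size to be run.

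The text also describes each efficacy hypothesis as powered to about 99%, which suggests that risk is spread evenly over seven tests. At the planned size the five acuity and CLUE tests contribute almost none of it.

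**Working it through.** **Inputs.** Thresholds, n and powers from Table 6; means and SDs from Table 7; one-sided alpha 0.025; planned n of 140, 84 and 56 from 4.1. Section 14.2 says the acuity calculations were "carried out separately using one-sided, one-sample mean t-test, with a one-sided Type I error rate of 0.025" and describes the same test for CLUE vision.

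**Step 1: reproduce the five t-test powers.** Let d = |mean − threshold| / SD and λ = d√n. Power is the probability that a noncentral t with n−1 degrees of freedom and noncentrality λ exceeds the 0.975 quantile of the central t. For distance acuity, d = 0.13/0.078 = 1.667 and λ = 1.667 × √9 = 5.00, giving power 0.9914.

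| Endpoint | Threshold | Mean (SD) | Table 6 n | Table 6 power | Recomputed | Planned n | Power at planned n |
|---|---|---|---|---|---|---|---|
| Distance VA | <0.00 | −0.13 (0.078) | 9 | 99.1% | 0.9914 | 140 | >0.999999 |
| Intermediate VA | <0.17 | −0.05 (0.092) | 6 | 99.5% | 0.9953 | 140 | >0.999999 |
| Near VA | <0.17 | 0.07 (0.120) | 29 | 99.1% | 0.9911 | 140 | >0.999999 |
| CLUE vision, myopes | >41 | 57.97 (20.282) | 29 | 99.2% | 0.9915 | 84 | >0.999999 |
| CLUE vision, hyperopes | >36 | 54.32 (19.506) | 23 | 99.0% | 0.9904 | 56 | >0.999999 |

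All five match. Each Table 6 n is the smallest that reaches 99%.

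**Step 2: reproduce the combined figures**, taking each >99% as 0.99.
- Efficacy: 0.991 × 0.995 × 0.991 × 0.992 × 0.990 × 0.99 × 0.968 = 0.920
- Safety: 0.893 × 0.99 = 0.884
- Overall: 0.920 × 0.884 = 0.813

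These are the stated 92%, 88% and 81%. The five small-n factors multiply to 0.960 and the four n=140 factors to 0.847.

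**Step 3: put every factor at the planned n.** The five t-test powers now multiply to 0.9999996.

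| Value used for >99% | Efficacy | Overall |
|---|---|---|
| 0.99 | 0.99 × 0.968 = 0.958 | 0.958 × 0.893 × 0.99 = 0.847 |
| 1.00 | 0.968 | 0.968 × 0.893 = 0.864 |

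With 0.99 used on both sides, the change due to sample size alone is 0.920 to 0.958 for efficacy and 0.813 to 0.847 overall, or 3.8 and 3.4 points.

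**Step 4: how far this depends on independence.** Adding the failure probabilities at the planned n (0.010 + 0.032 + 0.107 + 0.010 = 0.159) gives at least 0.841 under any dependence between endpoints. The lower bound of 81% therefore does not rest on independence.

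**Step 5: which toric endpoint is at 96.8%.** The plan's correlated-binary model was run with 140 pairs of eyes, between-eye correlation 0.70 and the beta(0.5, 0.5) prior from 14.2. It gives 0.961 for absolute rotation at the assumed 90.2% rate and about 1.00 for stability at the assumed 99%. Table 6 prints >99% for rotation and 96.8% for stability, so those two entries may be interchanged. Both products are unaffected. The same run gives 0.886 for slit-lamp findings, close to the stated 89.3%; other vague priors move that power between about 82% and 94%.

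**The case against.** The best defence is that sizing each continuous endpoint to about 99% and multiplying is a deliberate, conservative device. The statement before Table 6 says at least 81%, which is true. Table 6 prints the n beside every power, so where the risk sits can be read from it, and efficacy and safety are reported separately. All of this stands. The fault is confined to the later statement, which drops the lower-bound wording and gives about 92% and about 81% as the study's power.

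Four stronger readings are tempting and are not supported:

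- **The trial is underpowered, or N is wrong.** The error runs the other way.
- **The combined power rests on tiny samples throughout.** Four of the nine factors, including the two that limit power, are already at n=140 and account for most of the shortfall.
- **The right answers are simply 97% and 86%.** Those are the upper ends. They change >99% from 0.99 to 1.00, so part of the apparent gap comes from that switch.
- **Power is higher still because 155 are enrolled.** Section 4.1 treats ineligible subjects as screen failures, and the safety population in 14.3 includes only those given a lens. The documents do not support counting all 155.

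The slit-lamp power also depends more on the prior than the overall figure does on the mixed sample sizes. The restated 85-86% is therefore what the plan's inputs imply, and no firmer than they are.

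**Conclusion.** The combined powers of about 92% and about 81% are not those of the planned design. At 140 completers (84 and 56 by stratum) the plan's own inputs give about 96-97% for efficacy and 85-86% overall, roughly 3 to 5 points above the stated overall figure depending on how >99% is read. This assumes the Table 7 means and SDs, the plan's t-test approximation, the Table 6 binary powers and independent endpoints. Sample size, tests and decision rules are unaffected, so this is a minor correction.

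The remaining risk lies mainly in slit-lamp findings (89.3%) and the one toric endpoint at 96.8%. A reader might name absolute rotation as that endpoint; as printed, Table 6 says stability, and the question stays open until the two rows are checked.

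Two nearby statements in 14.2 also conflict with Table 6. One claims at least 99% power for every co-primary and secondary endpoint; the other says at least 99% of the slit-lamp intervals had an upper bound below 5%. Table 6 gives 96.8% for stability and 89.3% for slit-lamp findings.

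**What to change.** 1. Add to Table 6 the power at the planned n for every row (140 overall, 84 myopes, 56 hyperopes). The n needed for 99% can stay as a separate column.
2. Replace about 92% and about 81% with about 96-97% and about 85-86%, stating that independence is assumed and how >99% was entered. Alternatively, keep 92% and 81% but label them as lower bounds everywhere.
3. Check the simulation output for the rotation and stability rows and correct them if interchanged. Then state that slit-lamp findings and the toric endpoint at 96.8% drive the overall power.
4. Reconcile both claims of at least 99% with the 89.3% and 96.8% in Table 6.

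The cost is restated figures and a few sentences in 14.2, with no change to enrolment, analyses or conduct.

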2.2.3. Secondary Efficacy Endpoints

- Subjective Handling Scores at the 2-Week follow-up visit will be assessed using the CLUETM questionnaire. The overall mean handling score is a continuous endpoint.
- Subjective Comfort Scores at the 2-Week follow-up visit will be assessed using the CLUETM questionnaire. The overall mean comfort score is a continuous endpoint.
- Subjective Vision Scores at the 2-Week follow-up visit will be assessed using the CLUETM questionnaire. The overall vision score is a continuous endpoint.
- Lens Fit Success is the number of lenses needed to fit (optimize) the subject's vision. Lens fit success is a binary endpoint where, Y=1 if a subject's vision was optimized in four lenses or less, and Y=0, otherwise. The number of lenses needed is determined using lens selection data from both Visit 1 and Visit 2.

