2.3.3. Secondary Efficacy Hypotheses

A fixed sequence approach will be used to control the type I error. The order of testing secondary hypotheses are as follows:

- 1. After approximately 2-Weeks of wear, the mean CLUE *handling* score of the Test lens will be statistically significantly better (greater) than 46 for the hyperope population.
- 2. After approximately 2-Weeks of wear, the mean CLUE *comfort* score of the Test lens will be statistically significantly better (greater) than 38 for the hyperope population.
- 3. After approximately 2-Weeks of wear, the mean CLUE *handling* score of the Test lens will be statistically significantly better (greater) than 55 for the myope population.
- 4. After approximately 2-Weeks of wear, the mean CLUE overall *quality of vision* score of the Test lens will be statistically significantly better (greater) than 41 for the hyperope population.
- 5. After approximately 2-Weeks of wear, the mean CLUE *comfort* score of the Test lens will be statistically significantly better (greater) than 51 for the myope population.
- 6. After approximately 2-Weeks of wear, the mean CLUE overall *quality of vision* score of the Test lens will be statistically significantly better (greater) than 46 for the myope population.
- 7. The percentage of subjects who are fit with the optimized lens pair in 4 lenses or less will be statistically significantly better (greater) than 90%.

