refraction are not acceptable then a lens modification must be made. If modifications are not needed, proceed to step 2.22. Up to two attempts at changes are permitted, if necessary, in order to achieve an acceptable distance and near binocular performance for the subject.		Modification (if	-	
 modification must be made. If modifications are not needed, proceed to step 2.22. Up to two attempts at changes are permitted, if necessary, in order to achieve an acceptable distance and near binocular performance for the subject. 		required)		
are not needed, proceed to step 2.22. Up to two attempts at changes are permitted, if necessary, in order to achieve an acceptable distance and near binocular performance for the subject.			-	
Up to two attempts at changes are permitted, if necessary, in order to achieve an acceptable distance and near binocular performance for the subject.				
if necessary, in order to achieve an acceptable distance and near binocular performance for the subject.			are not needed, proceed to step 2.22.	
if necessary, in order to achieve an acceptable distance and near binocular performance for the subject.			Up to two attempts at changes are permitted.	
performance for the subject.				
			performance for the subject.	
Nalaot the reagon(g) for long abange (galaot			Select the reason(s) for lans change (select	
Select the reason(s) for lens change (select all that apply):			· · · · · · · · · · · · · · · · · · ·	
The settled lens rotation is such that one of				
the other available lens cylinder axes would				

	V 13	sit 2: Treatment 1 Follow-Up 1	
Step	Procedure	Details	
		be better (use LARS rule to determine the	
		replacement lens cylinder axis)	
		 Power Modification needed 	
		 Unsatisfactory Vision 	
		Other (specify reason)	
		Note: switching to a non-multifocal lens per	
		Step 3 of the Fitting Guide is not an	
		available option in this study.	
2.13	Lens Selection (if	Select the lens power, based on the Fitting	Appendix
	required)	Guide for each eye needing optimization.	D
		Record the test lens parameters (power and	
		lot number).	
2.14	Lens Insertion (if	Subjects will insert the lens themselves. If	
2.14	required)	the lens is uncomfortable, inspect for damage	
	required)	and remove, reinsert or replace as necessary.	
		and remove, remisert of replace as necessary.	
		Damaged lenses will be stored in labeled vial	
		with saline solution, and clearly	

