The reference rate for lens fit success was based on the worst-case scenario of 99%, given the historical results show 100% (Table 6). Lens fit is a binary response and is defined as follows:

Lens Fit Success :
$$Y = \begin{cases} 1 & \text{if a subjects' vision is optimized in 2 pairs or less} \\ 0 & \text{Otherwise} \end{cases}$$

Historical data of the Test lens indicates there is an extremely high rate (100%) for lens fit success. Assuming a correlation of 0.70 between left and right eyes, a total of 5000 replicating trials were simulated with reference rate of 99% for the percentage of eyes optimized in 4 lenses (2 pairs) or less. Given the high event rate of the binary outcome, Y=1, each replicated sample was analyzed using a Bayesian beta-binomial model with correlated binary data (Diniz et al; 2010)¹⁴. A non-informative prior distribution, beta(1, 1) was used to model P_T (proportion of eyes with optimized in 4 lenses or less). For each simulated trial, the 95% central posterior credible interval (CrI) constructed for the percentage of eyes optimized in 4 lenses or less was calculated. The null and alternative hypothesis for determining statistical significance were $P_T \leq 90\%$ and $P_T > 90\%$, respectively. With the proposed sample size, the percentage of eyes optimized in 4 lenses or less has at least 99% power, i.e., 99% of the estimated 95% CrIs had the lower bound above 90%.

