The null and alternative hypothesis to test for superiority of the myopic subjects relative to the pre-defined threshold of 51 for the investigational lens is as follows:

$$\begin{array}{l} H_o: \mu_{Myopes} \leq 51 \\ H_A: \mu_{Myopes} > 51 \end{array}$$

Where μ_{Myopes} represents the population mean for the investigational lens after 2-weeks lens wear with respect to CLUE comfort scores for myopic subjects. The investigational lens will be declared statistically significantly greater than 51 if the one-sided p-values is below 0.025.

The null and alternative hypothesis to test for superiority of the myopic subjects relative to the pre-defined threshold of 46 for the investigational lens is as follows:

 $\begin{array}{l} H_o: \mu_{Myopes} \leq 46 \\ H_A: \mu_{Myopes} > 46 \end{array}$

Where μ_{Myopes} represents the population mean for the investigational lens after 2-weeks lens wear with respect to CLUE vision scores for myopic subjects. The Test lens will be declared statistically significantly greater than 46 if the one-sided p-values is below 0.025.

Lens Fit Success (Number of lenses required to achieve lens optimization)

Number of lenses required to achieve lens optimization will be analyzed using a Bayesian betabinomial model with correlated binary data¹⁴.

Bayesian Estimation and Statistical Evaluation of Hypothesis:

Superiority of the Test lens relative to the pre-defined threshold with respect to unacceptable lens fitting will be evaluated using Bayesian statistics. The null and alternative hypotheses for evaluating superiority of the investigational lens relative to 90% are as follows:

$$H_0: p_T \le 90\%$$

 $H_A: p_T > 90\%$,

where p_T is the probability of event (i.e., proportion of subjects to achieve optimization in 4 lenses or less while wearing the test lens). Based on Bayesian posterior probability distribution of the proportion p_T , superiority is interpreted as 95% probability of the Test lens being statistically greater than the pre-defined threshold of 90% (i.e., $p_T > 0.90$) with respect to unacceptable lens fitting rate. If the upper bound of the 95% central posterior credible interval is above 0.90, it can be concluded that there is 95% probability that the investigational lens is superior to the 90% threshold (statistically better) based on the observed sample.

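### Lens fit success is defined per subject but powered and modelled per eye, and its four-lens and two-pair counting rules can disagree

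*Combined protocol and SAP*

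**What the plan says.** **Unit.** Section 2.2.3 gives one result per subject: "Lens fit success is a binary endpoint where, Y=1 if a subject's vision was optimized in four lenses or less", counted from lens selection data at Visits 1 and 2. The seventh secondary hypothesis in 2.3.3 concerns "The percentage of subjects who are fit with the optimized lens pair in 4 lenses or less", to be shown greater than 90%. Section 14.6 defines the tested parameter as the "proportion of subjects to achieve optimization in 4 lenses or less while wearing the test lens".

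Section 14.2 first defines the outcome by subject, "if a subjects' vision is optimized in 2 pairs or less", but then simulates trials at a 99% rate for the "percentage of eyes optimized in 4 lenses (2 pairs) or less", assumes a correlation of 0.70 between left and right eyes, and defines its parameter as a proportion of eyes. Table 7 lists the historical 100% under a column headed as a mean or a percentage of eyes. Section 14.6 names the correlated-binary beta-binomial model, which 14.5.1 and 14.5.2 build as the sum of a left-eye and a right-eye response.

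**Counting rule.** It is four lenses in 2.2.3, 2.3.3 and the parameter definition in 14.6. It is two pairs in the 14.2 formula. It is four lenses with two pairs in brackets in the 14.2 text and in the last paragraph of 14.6. Section 7.2 (steps 1.34 and 2.21) allows a lens to be changed in one eye only.

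**The concern.** The correlated model needs two binary results per subject. The endpoint supplies one, a total over both eyes, and nothing says how an eye-level success would be derived from it. Whoever programs the analysis must therefore choose: score each eye separately, or enter the subject's result for both eyes. The first choice tests a proportion of eyes, which is not the quantity in the hypothesis and is never lower than the proportion of subjects in whom both eyes succeed.

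The two counting rules add a second choice, which decides whether some subjects count as successes at all. Both should be settled before data are seen, because this test supports a claim about how easily the lens is fitted.

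**Working it through.** **Inputs.** 140 completers and one-sided 0.025 (14.2, 14.4); threshold 90% (2.3.3, Table 6); assumed rate 99%, correlation ρ = 0.70, beta(1,1) prior on the proportion, and success when the lower bound of the 95% credible interval exceeds 90% (14.2); model and beta(0.5,0.5) prior on ρ (14.5.1, 14.5.2).

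**1. The plan's figure, by eye.** With eye-level rate p, the model gives each subject:
- both eyes succeed: (1−ρ)p² + ρp
- one eye succeeds: 2(1−ρ)p(1−p)
- neither succeeds: (1−ρ)(1−p)² + ρ(1−p)

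In 5,000 simulated trials of 140 subjects at p = 0.99 and ρ = 0.70, every trial passed, so power is about 100%. This agrees to within 2 points with the 99.8% in Table 6 and did not change under the other priors tried.

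**2. By subject.** X ~ Bin(140, p), with posterior beta(X+1, 141−X). The 2.5% quantile is 0.891 at X = 132 and 0.9004 at X = 133, so success needs at least 133/140.
- P(X ≥ 133 | 0.99) = 99.99%
- P(X ≥ 133 | 0.98) = 99.3% (98% is assumed here, to show a range)
- P(X ≥ 133 | 0.90) = 2.57%

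With an exact (Clopper-Pearson) lower bound, 133 gives 0.8997, so success needs 134/140. Power at 99% is then 99.94% and type I error 1.09%.

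**3. Eyes scored separately.** Assume that subject success means both eyes succeed. The subject rate is then 0.3p² + 0.7p at ρ = 0.70.
- At p = 0.99: 0.3 × 0.9801 + 0.7 × 0.99 = 0.987. Subject-level power is 99.95%.
- At a subject rate of exactly 0.90: p = (−0.7 + √(0.49 + 4 × 0.3 × 0.9)) / (2 × 0.3) = (−0.7 + 1.253)/0.6 = 0.922. The eye-level test against 90% then passed in about 13% of 20,000 simulated trials. The subject-level test passes in 2.57%.

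**4. Subject result entered for both eyes.** No subject then has discordant eyes. With beta(1,1) or beta(0.5,0.5) on the proportion, the correlated model's cutoff is again 133/140, and its simulated type I error at 90% was 2.6%. With a nearly flat prior on the logit, the form that 14.5.1 uses, the cutoff is 132/140, where P(X ≥ 132 | 140, 0.90) = 5.3%. Section 14.6 states no prior for this endpoint.

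**5. Counting rules.**

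| Lenses, one eye + other | Four or fewer in total | At most two per eye |
|---|---|---|
| 1+1, 1+2, 2+2 | success | success |
| 1+3 | success | failure |
| any total above four | failure | failure |

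A total above four puts at least three lenses in one eye, so 1+3 is the only split on which the rules differ. It arises when one eye is changed twice and the other never.

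**The case against.** The strongest reply is that this is a wording fault with no shown effect. Section 14.6 does define its parameter per subject, and for this endpoint the eye wording sits in the sample-size text and the Table 7 heading. Lens selection is recorded for each eye, so per-eye counts exist. Power exceeds 99% in either unit. If the subject's result is entered for both eyes, the correlated model reproduces the subject-level cutoff under a beta prior. The documents treat four lenses and two pairs as synonyms, and give no frequency for the 1+3 split. Section 14.1 defers detail to a stand-alone SAP, and no later test depends on this one.

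Most of that stands, and it limits the size of the point. It does not remove it. Per-eye counts are not a per-eye success rule, and no rule for forming the pair is given. The agreement in step 4 depends on a coding choice and a prior that the plan does not state.

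A reader might go further and infer that each eye is allowed four lenses, so that the 90% threshold could hardly be missed. The documents do not support that: 14.2 and 14.6 both gloss four lenses as two pairs, which rules out four for a single eye. Nor do they support saying that the analysis certainly tests the wrong hypothesis, since 14.6 states the right parameter and attaches an ill-fitting model to it.

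**Conclusion.** The plan is inconsistent as written, at low to moderate severity. The unit conflicts between the definition and the power calculation, the named model does not fit one result per subject, and the counting rule has two non-equivalent forms. The sample size and the stated power are not in question.

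The effect on the test depends on implementation. The pass rate of about 13% at a true subject rate of 90% rests on three assumptions: eyes are scored separately, subject success means both eyes succeed, and ρ = 0.70. The second assumption corresponds to the two-per-eye rule, not to the total count in 2.2.3, so the figure illustrates the risk and does not predict the trial's error rate. If the subject result is entered for both eyes with a beta prior, the two tests agree. The effect of the 1+3 split cannot be sized from the documents.

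**What to change.** - Keep the definition in 2.2.3 and make it explicit: success if four or fewer study lenses in total, over both eyes and Visits 1 and 2, were needed to reach the optimized pair.
- Remove or align the wording on eyes and two pairs in 14.2, and on two pairs in 14.6.
- In 14.6, replace the correlated model with a single-proportion beta-binomial model on subjects, and name the prior.
- Require the lower bound of the 95% credible interval to exceed 90%. Section 14.2 uses the lower bound but 14.6 refers to the upper one; that is a separate discrepancy, best corrected in the same edit.
- Restate the power per subject. With beta(1,1), success needs 133/140, with power 99.99% at a 99% rate and type I error 2.57%. That is slightly above 2.5%. If strict control is wanted, the exact bound needs 134/140, with power 99.94% and type I error 1.09%.

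The cost is protocol and SAP wording and a simpler program, with no change to sample size or data collection. It should be settled before database lock.
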